**AMGEN** 

# 7.2.3 Treatment

The following procedures will be completed during the 28-week treatment period at the times designated in the Schedule of Assessments (Table 4). Study visits will occur weekly  $\pm$  3 days. All blood samples for laboratory assessments for hemodialysis subjects are to be collected prior to initiating the dialysis session during the visit. Cinacalcet will be dispensed to subjects to take home for daily administration at the conclusion of the study visit weekly.

The following procedures and assessments will be completed at the times designated in the Schedule of Assessment (Table 4, Section 7.1) and recorded on the eCRF:

- concomitant medications
- documentation of subject compliance with daily administration of cinacalcet
  - o patient diary review
  - o counts of returned bottles of tablets/capsules/suspension
- adverse events, including signs and symptoms of hypocalcemia, seizures, and infections
- serious adverse events
- ionized calcium
- central laboratory assessments including the following:
  - o serum calcium, serum albumin, and calculation of cCa, phosphorous
  - o iPTH
  - LFT (weeks 11 & 23)

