#### 6.2.3.1.1.1 Dosage Adjustments

The initial dose of cinacalcet and all subsequent doses will be calculated by the site staff and confirmed by the IVR/IWR system. Subjects from the SOC arm will start at the initial cinacalcet dose of 0.20 mg/kg/day, based on the subject's dry weight at day 1 of Study 20140159, rounded down to the lowest PSD.

Subjects from the cinacalcet arm with  $\leq$  14 days between the last dose of cinacalcet treatment in Study 20130356 and day 1 of Study 20140159 will start cinacalcet dosing at the same dose they received at the completion of the EOIP visit and follow weekly dose adjustment based on the Table 1. For subjects from the cinacalcet arm with > 14 days between the last dose of cinacalcet treatment in Study 20130356 and day 1 of

AMGEN

Page 26 of 79

Page 27 of 79

Study 20140159, the initial dose of cinacalcet will be 0.20 mg/kg/day, based on the subject's dry weight at day 1 of 20140159, rounded down to the lowest PSD, will be assigned.

Dose adjustments for subjects receiving cinacalcet will be assessed at each weekly visit during the treatment period. The daily dose of cinacalcet may only be increased at monthly titration visits (week 4, 8, 12, 16, 20, and 24); it can't be increased at any other time during the treatment period. At all weekly visits (including week 4, 8, 12, 16, 20, and 24), the dose may be maintained, reduced or withheld based upon the dose adjustment criteria in Table 1.

If any of the criteria for dose withholding are met at any time during the trial, including between scheduled study visits (ie, unscheduled), the dose of cinacalcet is to be withheld until all of the following criteria are met:

- central laboratory corrected calcium value is >8.4 mg/dL
- iPTH is > 150 pg/mL
- ionized calcium is >1.05mmol/L
- subject has no symptoms of hypocalcemia
- subject doesn't have any ongoing adverse event(s) which warrant withholding of cinacalcet.

If a subject dose is being withheld, ionized calcium levels should be assessed weekly until an ionized calcium of >1.05 mmol/L is obtained, at which point, cCa and iPTH should be assessed by the central laboratory.

Once all the restart criteria above are met, cinacalcet may be restarted at one PSD below the previous dose received. Subjects receiving the lowest PSD (2.5 mg) who require a dose reduction will have their dose withheld until the criteria for maintaining or increasing the dose are met, at which time they will restart dosing at 2.5 mg/day.

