#### 7.2 General Study Procedures

All on-study visits and dosing should be scheduled from day 1. Week 1 begins one week after the day 1 visit. It is important to perform study assessments and obtain samples at the time points outlined in the Schedule of Assessments in Section 7.1.

The duplicate study assessments will be collected once for both studies as described in Section 7.2.2.

When it is not possible to perform a study visit at the specified time point, the visit may be performed within  $\pm$  3 days. If a study visit is missed, subsequent visits should resume on the original visit schedule. Missed assessments at prior visits should not be duplicated at subsequent visits.

With the exception of screening assessments, all study procedures for a visit must be completed on the same day.

It is the responsibility of the investigator to ensure that all procedures are performed according to the protocol.

Any blood or serum collected according to the Schedule of Assessments may be analyzed for any of the tests outlined in the protocol and for any tests necessary to ensure subject safety. This includes testing to ensure analytical methods produce reliable and valid data throughout the course of the study. This may also include, but is not limited to, investigation of unexpected results, incurred sample reanalysis, and analyses for method transfer and comparability.

Details regarding each type of procedure are provided in Section 7.3

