# 7.2.1 Screening and Enrollment

The following procedures are to be completed during the screening period at time points designated in the Schedule of Assessments (Section 7.1, Table 4):

- Confirmation that the Informed Consent Form and Assent Form (if applicable)
   have been signed
- Registration of the subject in the IVR/IWR system
- Serum pregnancy test
- Serum calcium, serum albumin, and calculation of cCa, phosphorus
- iPTH

# 7.2.2 Day 1

The following day 1 procedures are also required for the EOIP study visit for Amgen Study 20130356 and End of Study visit for Study 20110100 except where indicated. These procedures should not be duplicated and may be collected once where study visits overlap and entered onto the appropriate eCRF once eligibility for this study has been confirmed:

- 12-lead ECG
- physical exam
- dry weight
- height/Tanner stage
- dialysate calcium, type of dialysis
- blood pressure, heart rate
- ionized calcium
- central laboratory assessments including the following
  - $\circ$   $\,$  serum calcium, serum albumin, and calculation of cCa, phosphorus  $\,$
  - o iPTH
  - liver Function Tests (LFT)
  - o chemistry panel
  - o hematology panel
  - 25 (OH) Vitamin D (not required for subjects from 20110100)
  - o total & bioavailable testosterone (male)
  - bone specific alkaline phosphatase (BALP), cross-linked N-telopeptides of type 1 collagen (NTx), type 1 collagen cross-linked telopeptide (CTx), amino terminal propeptide of type 1 collagen (P1NP), FGF23 (not required for subjects from 20110100).

The following day 1 procedures will be recorded on the day 1 eCRF:

- medical history (including ongoing AEs/SAEs from studies, 20130356 and 20110100)
- concomitant medications
- adverse event reporting
- serious adverse event (SAE) reporting
- ediary provision and training (all subjects)

Following completion of the day 1 visit assessments, eligibility, dry weight, and enrollment will be entered in the IVR/IWR system, as applicable. Following enrollment in the IVR/IWR system, IP will be dispensed and recorded on the day 1 eCRF.

CONFIDENTIAL

Page 46 of 79

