# 7.2.4 End of Investigational Product

The end of investigational product (EOIP) visit will occur at week 28. The procedures to be performed at this visit include the following:

- 12-lead ECG
- blood pressure, heart rate
- concomitant medications
- · documentation of subject compliance with daily administration of cinacalcet
  - o patient diary review
  - o counts of returned bottles of tablets/capsules/suspension
- adverse events, including signs and symptoms of hypocalcemia, seizures, and infections
- serious adverse events

CONFIDENTIAL

Page 47 of 79

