**AMCEN** 

#### Page 48 of 79

- ionized calcium
- central laboratory assessments including the following:
  - o serum calcium, serum albumin, and calculation of cCa, phosphorus
  - o chemistry panel
  - o hematology
  - 25 (OH) Vitamin D (not required for subjects from 20110100)
  - o iPTH
  - total and bioavailable testosterone (male)
  - BALP, NTx, CTx, P1NP, FGF23 (not required for subjects from 20110100)

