# 7.2.5 Early Termination

Subjects who discontinue participation in the study prior to week 28 will be asked to complete an early termination visit and should have all EOIP and EOS evaluations performed as outlined in the Schedule of Assessments and in Sections 7.2.4 and 7.2.6.

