## 7.3.10 Adverse Events

Adverse events will be collected in the eCRF for each subject at all study visits. Targeted questions regarding hypocalcemia, seizures and infections will be asked and data will be entered into the eCRF at each study visit.

All clinically significant (according to the investigator's judgment), laboratory abnormalities will be reported as adverse events. In assessing clinical significance of a low serum calcium value, the investigator should consider factors such as presence of clinical symptoms associated with hypocalcaemia, dose adjustment of cinacalcet or concomitant medications (eg, vitamin D, phosphate binders). In addition, the investigator should indicate on the eCRF whether hypocalcemia was symptomatic, and if so provide the accompanying symptoms.

Serious adverse events that occur in a subject from the date of the first dose through 30 days after the last dose of IP will be recorded in the adverse event eCRF. All adverse events that occur from the date of the first dose through 30 days after the last dose of IP will be recorded in the adverse event eCRF. Refer to Section 9 for additional information.

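### Completers have no scheduled on-drug ALT, AST or ALP after week 23: the week 28 end-of-treatment draw includes bilirubin but not the liver enzymes

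*Protocol*

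**What the plan says.** Protocol Table 4 and the visit lists in Section 7.2 agree on the liver tests:

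- Day 1 (7.2.2) includes "liver Function Tests (LFT". Screening includes them only if more than 14 days have passed since the last parent-study visit.
- The treatment period (7.2.3) has "LFT (weeks 11 & 23".
- On the end-of-treatment visit, 7.2.4 states: "The end of investigational product (EOIP) visit will occur at week 28". Its central-laboratory list has calcium, albumin and phosphorus, the "chemistry panel", hematology, iPTH and several others, but no liver tests. The Table 4 cell is empty too.
- Week 32 (7.2.6), after the 4-week off-drug period, has liver tests again.

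Table 5 puts ALT, AST and alkaline phosphatase under liver function tests and total bilirubin under serum chemistry. Week 28 therefore yields bilirubin but not the three enzymes.

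Dose increases are allowed at "monthly titration visits (week 4, 8, 12, 16, 20, and 24", so the last one comes a week after the last on-drug enzyme test. Subjects who stop before week 28 "should have all EOIP and EOS evaluations performed as outlined in the Schedule of Assessments" (7.2.5), and so do have liver tests at termination.

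SAP 10.7.2 gives one-way shift tables for ALT, AST, total bilirubin and alkaline phosphatase, using the worst grade at any visit up to end of study.

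**The concern.** The primary objective is long-term safety, and drug-related hepatic disorders are a named event of interest in the primary endpoint (Protocol 10.4.2, SAP 6.4). Completers have the longest exposure in this study, yet they are the subjects with no enzyme value at the end of treatment.

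Two features suggest an omission. Week 28 is the only visit with chemistry and no liver tests: screening (when required), day 1 and week 32 have both. The week 28 central-laboratory list is also the day 1 list with that one item missing. No reason is given.

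Two things are at stake. First, an enzyme rise that starts after week 23, causes no symptoms and resolves before week 32 cannot enter the ALT, AST or ALP shift tables from scheduled data. It would also be lost from the hepatic event of interest, but only if the investigator would have called it clinically significant, since it is then that "laboratory abnormalities will be reported as adverse events" (7.3.10; 9.2.1 leaves out the rest). Second, the stopping rule in 6.3.1 and the reporting rule in Appendix A need AST or ALT raised together with bilirubin or INR. A raised bilirubin at week 28 cannot be read against those rules without an added test.

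**Working it through.** **Inputs.** Target days from the SAP 6.2 window table for other laboratory tests: week 11 = 78, week 23 = 162, week 28 = 197, week 32 = 225. Visit tolerance is ±3 days (Protocol 7.2). Enrollment is at most 78.

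**Length of the gap**
- On drug with no later on-drug enzyme value: 197 − 162 = 35 days. With visit tolerance, (197 − 3) − (162 + 3) = 29 days to (197 + 3) − (162 − 3) = 41 days.
- Share of treatment: 5/28 = 17.9%.
- Time off drug at the next test: 225 − 197 = 28 days (22 to 34 with tolerance).
- Enzyme values after day 1: weeks 11, 23 and 32, so three, two of them on drug. With week 28 added: four, three on drug.

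**What a week 28 test would catch.** The documents give no liver-event rate, onset pattern or duration, so this part rests on an assumption: onset is uniform over the 35 days after week 23, and the rise lasts d days. Count days from week 23, so that week 28 is day 35 and week 32 is day 63.
- Current schedule: the rise is seen only if onset + d ≥ 63. The probability is 0 for d ≤ 28 and (d − 28)/35 for d from 28 to 63.
- With week 28 added: the rise is seen if onset + d ≥ 35. The probability is d/35 up to d = 35, then 100%. A rise that is over by week 28 is also over by week 32, so week 32 adds nothing further.

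| Duration d (days) | Current schedule | Week 28 added |
|---|---|---|
| 7 | 0% | 20% |
| 14 | 0% | 40% |
| 21 | 0% | 60% |
| 28 | 0% | 80% |
| 35 | 20% | 100% |
| 42 | 40% | 100% |
| 49 | 60% | 100% |
| 56 | 80% | 100% |
| 63 | 100% | 100% |

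**The same test over the whole treatment period.** With onset uniform over all 196 treatment days and d = 7, 14, 21 or 28, weeks 11 and 23 catch 2d/196 = 7%, 14%, 21% and 29%. Adding week 28 gives 3d/196 = 11%, 21%, 32% and 43%.

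**Assays added.** 3 × 78 = 234 at most.

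**The case against.** The strongest reply is that little is lost. Dosing has ended by week 28, so the result cannot change treatment. Persistent injury shows at week 32 and still triggers Appendix A follow-up and reporting. Symptoms are asked about at every visit, and under 7.2 blood already collected "may be analyzed for any of the tests outlined in the protocol and for any tests necessary to ensure subject safety". All of this stands, and it is why the point is minor.

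Liver sampling is also sparse throughout: the intervals between scheduled tests are 77, 84 and 63 days, and the one at issue is the shortest. Over the whole treatment period most brief rises are missed with or without week 28. This stands too. The detection table is conditional on onset in the last five weeks and does not describe liver monitoring as a whole.

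The schedule may have been chosen: the amendment log shows the liver-test row revised twice with week 28 left blank, and Protocol 2.4 says blood volumes are kept small. That is possible, but no document gives a reason for leaving the enzymes out of this one chemistry draw.

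A reader might infer three stronger things that the documents do not support:
- That the liver shift tables have no end-of-treatment value at all. The total bilirubin row has one at week 28, and the week 32 enzymes count because the tables take the worst grade up to end of study.
- That late rises always escape. The 0% holds only for durations up to 28 days; longer ones are increasingly caught at week 32.
- That the week 24 dose increase carries a liver risk. The documents give no dose relation, so week 24 bears on timing only.

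**Conclusion.** The gap is real and minor. In completers the ALT, AST and ALP shift tables have no scheduled on-drug value from the last 5 of 28 treatment weeks, and the week 28 bilirubin cannot be judged against concurrent AST or ALT under the liver-injury criteria. What can be missed is a symptom-free enzyme rise that begins after week 23 and is gone by week 32. No endpoint or table becomes impossible to compute. The schedule itself is read directly from the protocol; the detection figures rest on the assumed uniform onset and fixed duration. The number of events affected cannot be stated, because no liver-event rate is given. Early terminators are not affected.

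**What to change.** Add ALT, AST and ALP to the week 28 central-laboratory panel: one mark in Table 4 and one line in 7.2.4. Run them on the chemistry sample already drawn, which 7.2 permits.

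First confirm with the central laboratory that the sample suffices for the smallest subjects (dry weight from 7 kg for those from Study 20110100). If it does not, omit the added assays for those subjects rather than draw more blood. The day 1 draw already combines liver tests with every test on the week 28 list, which suggests that it is feasible, but the laboratory manual is not available to show it.

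The cost is at most 234 extra assay results and the volume check. No visit is added, and the SAP needs no change because its shift tables already accept any visit up to end of study.

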# 7.2.4 End of Investigational Product

The end of investigational product (EOIP) visit will occur at week 28. The procedures to be performed at this visit include the following:

- 12-lead ECG
- blood pressure, heart rate
- concomitant medications
- · documentation of subject compliance with daily administration of cinacalcet
  - o patient diary review
  - o counts of returned bottles of tablets/capsules/suspension
- adverse events, including signs and symptoms of hypocalcemia, seizures, and infections
- serious adverse events

CONFIDENTIAL

Page 47 of 79

**AMCEN** 

#### Page 48 of 79

- ionized calcium
- central laboratory assessments including the following:
  - o serum calcium, serum albumin, and calculation of cCa, phosphorus
  - o chemistry panel
  - o hematology
  - 25 (OH) Vitamin D (not required for subjects from 20110100)
  - o iPTH
  - total and bioavailable testosterone (male)
  - BALP, NTx, CTx, P1NP, FGF23 (not required for subjects from 20110100)

# 7.2.5 Early Termination

Subjects who discontinue participation in the study prior to week 28 will be asked to complete an early termination visit and should have all EOIP and EOS evaluations performed as outlined in the Schedule of Assessments and in Sections 7.2.4 and 7.2.6.

#### 7.2.6 End of Study Visit

Subjects will complete an EOS visit at week 32 within +/- 3 days of the scheduled visit date or at early termination. The following evaluations apply to the EOS visit:

- physical exam
- dry weight
- height/Tanner stage
- 12-lead ECG
- blood pressure, heart rate
- concomitant medications
- adverse events, including signs and symptoms of hypocalcemia, seizures, and infections
- serious adverse events
- central laboratory assessments including the following:
  - o serum calcium, serum albumin, and calculation of cCa, phosphorous
  - o chemistry panel
  - o CBC, LFTs
  - 25 (OH) Vitamin D (not required for subjects from 20110100)
  - o iPTH
  - o serum pregnancy test (female of child bearing potential)

Page 49 of 79

# 7.3 Description of General Study Procedures

#### 7.3.1 Informed Consent/Assent

All subjects must have a parent or legal representative sign and personally date the IRB/IEC approved informed consent form before any study specific procedures are performed. In addition, subjects must sign and personally date the assent form when applicable prior to the performance of any study specific procedures. See Section 11.1 for further details.

# 7.3.2 Demographic Data

Demographic data including sex, date of birth, race, and ethnicity will be collected in order to study their possible association with subject safety and treatment effectiveness. These data will be transferred from the studies 20130356 and 20110100.

# 7.3.3 Medical and Surgical History

The subject's complete medical and surgical history will be reviewed on day 1. The investigator or designee will collect a complete medical and surgical history for conditions that started within 5 years of the date of enrollment, including information on the subject's concurrent conditions. Ongoing adverse events and serious adverse events in studies 20130356 and 20110100 will be entered as concurrent conditions on the medical history form. This information will be recorded on the medical history eCRF for subjects enrolled into the study.

#### 7.3.4 Physical Exam, Height, Tanner Stage, Dry Weight

A physical exam will be performed on day 1. Breast, genital, and rectal examinations are not required for any study visit unless specific evaluation is warranted.

The physical examination at the EOS visit will consist of a follow-up examination to monitor for any changes from the day 1 physical examination. Any clinically significant changes in the physical examination per the investigator's opinion should be recorded on the adverse event eCRF.

Information regarding the subject's residual urine output will be collected on day 1.

Height will be collected on day 1 and at the EOS visit and should be measured with the subject's shoes removed.

Tanner stage will be determined on day 1 and at the EOS visit and recorded in the eCRF.

AMGE

Page 50 of 79

The subject's dry weight should be collected at day 1 and at the EOS visit post-dialysis for hemodialysis subjects and at the study visit, while the peritoneal cavity is empty, for peritoneal dialysis subjects. For all subjects the weight is to be measured with the subject wearing light clothing and with his/her shoes removed.

#### 7.3.5 Blood Pressure and Heart Rate

The blood pressure should be taken with the subject's arm supported at heart level using the appropriate sized cuff with the subject comfortably seated in a chair with his/her back supported and both feet on the ground. Subjects should be resting quietly for at least 5 minutes before the blood pressure and heart rate are measured. For subjects receiving hemodialysis, blood pressure and heart rate are to be measured at the conclusion of the dialysis session. For subjects receiving peritoneal dialysis, blood pressure and heart rate are to be measured at the conclusion of the dialysis session. For subjects receiving peritoneal dialysis, blood pressure and heart rate are to be measured during the study visit. All measurements will be recorded in the eCRF.

# 7.3.6 ECG

The subject must be in a supine position in a calm and resting state for at least 5 minutes before the ECG assessment is conducted. If the subject is unable to be in a supine position, he/she should be in the most recumbent position possible.

The ECG must include the following measurements: heart rate, QRS, QTc, and RR, QT intervals. For the purposes of this study, the QTc should be provided or calculated using Bazett's formula (QT/ $\sqrt{RR}$ ). For subjects receiving hemodialysis, the ECG is to be obtained prior to the initiation of the dialysis session. For subjects receiving peritoneal dialysis, the ECG is to be obtained during the study visit. All measurements will be recorded in the eCRF.

The investigator will review, sign, and date all ECGs. Once signed the original ECG tracing will remain in the subject's source documents. At the request of the sponsor, a copy of the original ECG will be made available to Amgen.

#### 7.3.7 Concomitant Medications

Concomitant medications will be collected beginning on day 1 through the end of study, and recorded in the eCRF for this study as described below.

The administration of vitamin D sterols, calcium supplementation, bisphosphonates, and phosphate binders, including the name of the medication, dose, unit, route, frequency, and start and stop dates of administration, will be collected.

AMGEN

Commercial cinacalcet is an excluded medication during this study (Section 6.6). For subjects who receive commercial cinacalcet, this will be documented as a protocol deviation and the name of the medication, dose, unit, route, frequency, and start and stop dates of administration will be collected.

Changes in dialysate calcium concentration during the course of the trial will be documented as a protocol deviation. For subjects in whom the dialysate calcium concentration changes during the course of the trial, the change in concentration and start date will be collected.

For all other concomitant medications, including over the counter and herbal medicines, the name of the medication, start and stop dates of administration will be collected.

